3.8.1. Screening (Day -30 to 0)

Any tests or procedures that are performed to confirm eligibility and are not standard of care must be performed AFTER the potential participant has signed the Informed Consent Form.

The following procedures are performed at the Screening visit:

- Obtain medical history and confirm potential participant's age
- Obtain written informed consent
- Perform urine pregnancy test for women of childbearing age
- Have potential participant complete the Ocular Surface Disease Index (OSDI) for each eye individually
- Perform Corrected Distance Visual Acuity
- Perform baseline TBUT test
- Perform baseline tear meniscus height test
- Administer fluorescein stain
- Perform slit-lamp biomicroscopy and assess corneal staining using the NEI grid and scoring system
- Perform baseline Schirmer test with topical anesthetic

If at any point in this process, the potential participant fails to meet eligibility, the process should be discontinued, and the potential participant should be recorded as a screen failure along with the reason.

3.8.2. Day 0

The following procedures are performed at the Day 0 visit:

- Have participant complete the OSDI for each eye individually
- Perform Corrected Distance Visual Acuity
- Instill HA device in inferior canaliculus of eye randomized to the device
- Instill saline in inferior canaliculus of fellow eye

3.8.3. Day 3 and 14

The following procedures are performed at the intermediate follow-up visits, Days 3 and 14:

- Have participant complete the OSDI for each eye individually
- Perform corrected distance visual acuity
- Perform slit-lamp biomicroscopy

3.8.4. Day 42

The following procedures are performed at the Day 30 visit:

- Have participant complete the Ocular Surface Disease Index (OSDI) for each eye individually
- Perform Corrected Distance Visual Acuity
- Perform TBUT test
- Perform tear meniscus height test
- Administer fluorescein stain
- Perform slit-lamp biomicroscopy and assess corneal staining using the NEI grid and scoring system
- Perform Schirmer test with topical anesthetic
- Remove device from inferior canaliculus by irrigation (if necessary for complete removal, hyaluronidase may be used)

3.9. Concomitant Medications and Therapies

All concomitant medications used within the 30 days prior to the screening visit, including medications used for relief of dry eye symptoms, will be documented on the case report form. Any initiation of new medications or changes to current medications during the course of the study should be recorded on the appropriate case report form. No other experimental drug or device should be used within 30 days prior to the Screening Visit or during the course of the clinical trial.

At the end of the Screening Visit, participants should be instructed not to use perfume or make-up on study days. Participants should also be instructed to refrain from administration of any chronic ophthalmic medication for two hours before their visit.

3.10. Participant Completion Procedures

A participant's participation in the study will be considered to have been completed when all assessments have been performed in accordance with the study protocol. At the end of the study, participants will be exited. If a participant chooses to discontinue the study before completion, the participant will be exited from the study.

3.11. Study Termination

The investigator reserves the right to discontinue the study for any safety or ethical reason at any time.

4. STATISTICS

4.1. Sample Size

This is a pilot, feasibility study. No sample size calculation has been performed.

4.2. Clinical Hypothesis

As a pilot, feasibility study, there is no clinical hypothesis.

4.3. Randomization

This is a single-arm, randomized, single-masked study in which one eye will receive the device in the lower canaliculus and the fellow eye will receive a sham injection of saline in the lower canaliculus. The eye which receives the device will be determined by a randomization sequence.

4.4. General Statistical Considerations

4.4.1. Participant Accountability and Missing Data

Participants who withdraw from the study will be tabulated with the reasons for the withdrawal.

4.5. Participant Demographic and Baseline Characteristics

The demographic and baseline characteristics of the study population observed will be presented descriptively. For continuous variables such as participant age, the mean, standard deviation (SD), median and range will be presented. For categorical variables such as gender, the number with or experiencing the condition, the total number evaluated, the percentage, and the exact 95% confidence interval on the percentage will be presented.

4.6. Effectiveness Analyses

The assessment of effectiveness will be based on the changes in the primary and secondary effectiveness endpoints from baseline to 6 weeks in the eye which receives the device as compared with the eye which receives the sham injection.

4.7. Safety Analyses

The primary safety endpoint will be the proportion of participants that experience one or more device-related adverse events. For corrected distance visual acuity, the proportion of participants with an improvement of more than two lines (11 or more letters), a worsening of more than two lines and a change of two lines or less will be summarized along with the exact 95% confidence interval at each visit. Biomicroscopy

results will also be presented as the proportion of participants with a clinically significant change from Baseline at each visit. Particular attention will be paid to any changes to the corneal surface. Summaries will be provided of the proportion of participants that experienced an unexpected device-related serious adverse event, the proportion of participants that experienced any adverse event and the proportion of participants that experienced each unique adverse event.

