3.6. Randomization

This is a single-arm, randomized, single-masked study in which one eye will receive the device in the lower canaliculus and the fellow eye will receive a sham injection of saline in the lower canaliculus. The eye which receives the device will be determined by a randomization sequence. The participant will remain masked as to which eye received the device and which eye received the sham.

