6. ADVERSE EVENTS AND SERIOUS ADVERSE EVENTS

6.1. Definitions

Adverse Event (AE): An adverse event is defined as any untoward medical occurrence, unintended disease or injury, or any untoward clinical signs (including an abnormal laboratory finding) in participants, users or other persons whether or not related to the investigational medical device. This includes events related to the investigational device or any procedures involved (any procedure in the study protocol). For users or other persons this is restricted to events related to the investigational medical device.

Serious Adverse Event (SAE): An AE should be classified as an SAE and reported as such if it meets one or more of the following criteria:

- It results in death (i.e., the AE actually causes or leads to death);
- It is life threatening (i.e., the AE places the participant at immediate risk of death);
- It requires or prolongs inpatient hospitalization. If a participant is hospitalized to undergo a medical or surgical procedure as a result of an AE, the event responsible for the procedure, not the procedure itself, should be recorded as the event. For example, if a participant is hospitalized to undergo coronary bypass surgery, the heart condition that necessitated the bypass should be recorded. Hospitalizations for diagnostic or elective surgical procedures or hospitalizations required to allow outcome measurement for the study should not be recorded as SAEs:

- It results in persistent or significant disability/incapacity (i.e., the AE results in substantial disruption of the participant's ability to conduct normal life functions);
- It results in a congenital anomaly/birth defect in a neonate/infant born to a mother exposed to the investigational device;
- It is considered a significant medical event by the investigator based on medical judgment (e.g. may jeopardize the participant or may require medical/surgical intervention to prevent one of the outcomes listed above);
- It is considered sight-threatening by the investigator.

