6.2. Adverse Event Assessment and Documentation

All participants who have been exposed to application of the study device should be evaluated for adverse events. All adverse events, regardless of severity and whether or not they are ascribed to the study device, should be recorded in the source documents and CRFs using standard medical terminology.

All adverse events should be evaluated beginning with onset and evaluation should continue until resolution is noted or until the investigator determines that the participant's condition is stable. The investigator should take appropriate and necessary therapeutic measures required for resolution of the adverse event. Any medication necessary for the treatment of an adverse event must be recorded on the concomitant medication CRF.

Pre-existing conditions or diseases that are chronic but stable should not be recorded on AE pages of the CRF but should be recorded in the medical history. Changes in a chronic condition or disease that are consistent with natural disease progression do not need to be recorded as adverse events and should not be recorded on the AE pages of the CRF. Clinical study staff should start assessing participants for AEs from the time of the first device application.

Whenever possible, recognized medical terms should be used when recording AEs. Colloquialisms and/or abbreviations should not be used. Only one medical concept, preferably a diagnosis instead of individual symptoms, should be recorded as the event. If more than one distinct adverse event occurs, each event should be recorded separately. However, if a constellation of signs and/or symptoms cannot be medically characterized as a single diagnosis or syndrome at the time of reporting, each individual event should be recorded as a separate AE. A diagnosis that is subsequently established should be reported as follow-up information. However, signs and symptoms that are considered unrelated to an encountered syndrome or disease should

be recorded as individual AEs (e.g. if congestive heart failure and severe headache are observed at the same time, each event should be recorded as an individual AE).

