6.3.3. Relatedness

The study investigator should evaluate if the AE is related to the use of the study device. Relationship is defined in the following manner:

Not related: Evidence indicates no plausible direct relationship to the study device such that:

- A clinically plausible temporal sequence is inconsistent with the onset of the AE and device application, and/or
- A causal relationship is considered biologically implausible, and/or
- The AE can be attributed to concurrent/underlying illness, other drugs or procedures.

Possibly related: Evidence indicates a possible relationship to the study device such that:

- The event occurs within a reasonable period of time relative to the application that makes a causal relationship possible, but plausible explanations may also be provided by other causes such as other drugs, products, chemicals, underlying disease, environment, etc., and/or
- The event is possibly related to the study application.

Related: Evidence indicates a reasonable temporal sequence of the event with the study device application exists or that the association of the event with study device application is unknown and the event is not reasonably supported by other conditions such that:

- There is a clinically plausible time sequence between onset of the AE and study device application a, and/or
- There is a biologically plausible mechanism for study application causing or contributing to the AE, and/or
- The AE cannot be reasonably attributed to concurrent/underlying illness, other drugs or procedures.

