If visual acuity is so poor that the participant cannot read any of the largest letters at 1 meter (i.e., the number of letters read correctly at 1 meter is zero), light perception should be tested with an indirect ophthalmoscope in a darkened room. The indirect ophthalmoscope light should be in focus at 3 feet with the rheostat set at maximum voltage. From a distance of 3 feet, the beam should be directed in and out of the eye at least four times and the participant should be asked to respond when s/he sees the light. If the examiner is convinced that the participant perceives the light, vision should be recorded as “light perception,” and, if not, vision should be recorded as “no light perception.”

Corrected Distance Visual Acuity Scoring Instructions

The ETDRS visual acuity worksheets are for clinic use only. The examiner records each letter identified correctly by circling the corresponding letter on the appropriate worksheet. The examiner records letters read incorrectly with an ‘X’ and leaves letters for which the participant makes no guesses unmarked. Each letter read correctly is scored as one point. After testing is completed, the score for each line (which is zero if no letters are read correctly) and the total score for each eye are recorded on the visual acuity worksheet. If testing at 1 meter is not required, 30 points are automatically scored for the 1-meter test. The total combined score (i.e., the sum of the 4- and 1-meter scores) are entered on the worksheet as the final visual acuity letter score.

Note: A clinically significant visual acuity decrease (defined as an increase of 0.22 or greater in logMAR score from Day 0) at a Follow-up visit will be considered an adverse event.

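### Section 4.7 counts ocular safety findings per participant without naming the eye, so the planned tables do not separate device eyes from sham eyes

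*Protocol*

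**What the plan says.** Sections 3.6 and 4.3 assign treatment to eyes within a participant: the device goes into one lower canaliculus, saline into the other, and a randomization sequence decides which. On masking, section 3.6 says "The participant will remain masked as to which eye received the device and which eye received the sham"; nobody else is stated to be masked. Section 4.6 bases effectiveness on the device eye against the sham eye.

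Section 4.7 plans these safety summaries:

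- Primary endpoint: participants with at least one device-related adverse event.
- Visual acuity: "For corrected distance visual acuity, the proportion of participants with an improvement of more than two lines (11 or more letters"), together with the proportions that worsened by more than two lines or changed by two lines or less, with exact 95% intervals at each visit.
- Biomicroscopy: "the proportion of participants with a clinically significant change from Baseline at each visit".
- Adverse events: participants with an unexpected device-related serious event, and "the proportion of participants that experienced any adverse event and the proportion of participants that experienced each unique adverse event".

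None of these items names an eye or mentions the sham.

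Elsewhere, section 9.2.2 has acuity scored eye by eye ("the total score for each eye are recorded on the visual acuity worksheet"). Section 6.1 says of the adverse event definition: "This includes events related to the investigational device or any procedures involved (any procedure in the study protocol"). Section 6.2 has all events recorded "regardless of severity and whether or not they are ascribed to the study device". Section 6.3.3 adds: "The study investigator should evaluate if the AE is related to the use of the study device".

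**The concern.** The randomized unit is the eye, but the safety tables are defined on the participant. Two things are at stake.

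First, the acuity table can be built in more than one way. A participant whose device eye loses 12 letters while the sham eye is stable belongs to two categories at once, and no rule says which eye counts.

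Second, the control is left unused where it would help most. Several anticipated events, such as irritation or subconjunctival hemorrhage, could follow the instillation itself, and the saline eye is the control for that. The primary endpoint rests on a relatedness judgement by an investigator who is not stated to be masked. The any-event and each-event proportions are the only planned adverse event summaries that do not depend on that judgement, and as written they do not show which eye was affected.

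**Working it through.** The Protocol gives no safety rate, power or expected event count to reproduce; section 4.1 states that no sample size calculation was done. The only numerical inputs from the document are up to 13 participants with a goal of 10 completers (Synopsis) and the three acuity categories (section 4.7). The event counts and rates below are assumed.

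**1. Acuity categories.** One eye falls into exactly one of three categories. Two eyes give 3 × 3 = 9 ordered device/sham pairs. In 3 pairs the eyes agree; in 9 − 3 = 6 they differ, and the participant then has no unique category. This counts possibilities and is not a probability.

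**2. Any adverse event, counted if either eye is affected.** This is one possible reading; the Protocol does not state it. Suppose 3 participants have an ocular event.

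| Denominator | Reported proportion | Exact (Clopper-Pearson) 95% CI |
|---|---|---|
| 13 | 3/13 = 23.1% | 5.0% to 53.8% |
| 10 | 3/10 = 30.0% | 6.7% to 65.2% |

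Each row is the same under quite different splits:

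| Device eyes affected | Sham eyes affected | Device minus sham, n = 13 | Device minus sham, n = 10 |
|---|---|---|---|
| 3 | 0 | +3/13 = +23.1 points | +3/10 = +30.0 points |
| 3 | 3 | 0 | 0 |
| 0 | 3 | −3/13 = −23.1 points | −3/10 = −30.0 points |

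**3. The same point in rates.** If the eyes are independent, the either-eye proportion is 1 − (1 − p_device)(1 − p_sham).

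- Device 10%, sham 30%: 1 − 0.9 × 0.7 = 37%.
- Device 30%, sham 10%: 1 − 0.7 × 0.9 = 37%.
- Both 10%: 1 − 0.9 × 0.9 = 19%, nearly twice the device-eye rate.

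If events overlap fully, the first two cases both give 30% and the third gives 10%. Reversing the treatments leaves the summary unchanged in either case.

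**4. What eye-specific reporting can deliver.** Each participant supplies one eye to each group, so the denominators stay at 10 to 13. With no events, the exact upper limit is 1 − 0.025^(1/n): 24.7% for n = 13 and 30.8% for n = 10. A paired exact (McNemar) test of 3 device-only against 0 sham-only participants gives p = 2 × 0.5³ = 0.25. The comparison can therefore only be descriptive.

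**The case against.** The best reply is that counting participants is not wrong in this design. Each participant has exactly one device eye, so the proportion of participants whose device eye worsened equals the proportion of device eyes that worsened. Section 4.7 is compatible with one row for device eyes and one for sham eyes, and the layout of by-eye tables is commonly left to a statistical analysis plan, which is not shown here. Participant-level adverse event counts are also conventional and are needed for non-ocular events. This is a small pilot without a hypothesis, eye-level acuity is collected, and listings for 13 people would show the detail.

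Part of this stands. The per-eye reading is possible, the data are not shown to lack laterality, and the illustrative counts are not evidence of any actual rate. It does not remove the point. Section 4.7 does more than leave table layout open: it fixes a unit and a set of categories, and without a named eye the acuity categories remain ambiguous. Taken as written, the all-event proportions count a participant affected only in the sham eye in the same way as one affected only in the device eye. An analysis plan could repair this only by adding a rule that the Protocol lacks.

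**Conclusion.** The concern holds and should be corrected, although it does not threaten the conduct of the study. It covers four summaries: acuity, biomicroscopy, any adverse event and each unique adverse event. The primary safety endpoint and the unexpected device-related serious event summary are outside the mixing problem, since sham-eye events should not be classed as device-related. Their limitation is a different one: they depend on attribution, with no sham-eye rate beside them.

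The ambiguity in the acuity categories follows from the text alone. The size given for the adverse event tables depends on the assumed 3 affected participants and on either-eye counting. Allocation is by a randomization sequence and acuity is scored per eye, so the acuity tables can be corrected without new data. For adverse events this depends on whether the form, which is not shown, captures the eye.

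**What to change.** Amend section 4.7 as follows:

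- Report acuity categories, clinically significant biomicroscopy changes and ocular adverse events (any, irrespective of relatedness, and each type) separately for device eyes and sham eyes, each with an exact 95% interval.
- Add a descriptive paired table for each finding: number of participants affected in the device eye only, the sham eye only, both and neither.
- Keep the participant-level device-related proportion as the primary safety endpoint, and keep participant-level proportions for non-ocular events.
- Ensure that the affected eye is recorded for every ocular adverse event, preferably by checking the form before enrollment.

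The cost is a few lines of protocol text, a few more tables and a form check. No visit or test is added. With 10 to 13 eyes per group the intervals will be wide, and the text should say that the comparison is descriptive.

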Single-Arm, Single-Center, Randomized, Single-Masked Study to Evaluate Restylane-Defyne for Canalicular Occlusion in Participants with Mild to Moderate Dry Eye Disease

Protocol Number: 0918

Protocol Date: July 9, 2018

Version 1.0

Revision History None

Principal Investigator
and Sponsor [name]
The Eye Care Institute
[name]
[name]

Monitor [name]
[name] Consulting, Inc.
[name]
[name]

PROTOCOL 0918 STUDY SYNOPSIS

Protocol Title	Single-Arm, Single-Center, Randomized, Single-Masked Study to Evaluate Restylane-Defyne for Punctal Occlusion in Participants with Mild to Moderate Dry Eye Disease
Study Period	Up to 3 months
Study Population	13 adult participants with mild to moderate dry eye disease
Primary Study Objectives	Safety and effectiveness assessments of Restylane-Defyne for punctal occlusion
Treatments	Participants will receive Restylane-Defyne in the inferior punctum of one eye and a sham injection in the inferior punctum of the fellow eye.
Study Design	Prospective, randomized, single-masked study with unilateral placement of Restylane-Defyne.
Sample Size	Up to 13 participants, with a goal of 10 participants finishing study.
Examination Schedule	Participants will have a Baseline Visit within 30 days prior to the initial device application. Device application will be initiated at Day 0 with follow-up visits at 3 days, 14 days and 42 days. Participants will exit the study after the 6-week visit exam.

Clinical Assessments

Assessments performed will include:

- Ocular Surface Disease Index questionnaire
- Slit-lamp biomicroscopy with grading of corneal staining
- Schirmer test with topical anesthetic
- Tear break-up time
- Tear meniscus height
- Corrected Distance Visual Acuity

Study Endpoints

- **Primary effectiveness endpoint**

Change in Schirmer score from baseline

- **Additional effectiveness endpoints**

Changes in OSDI score, corneal staining score, tear break-up time and tear meniscus height

- **Primary safety endpoint**

Proportion of participants that experience one or more device-related adverse events (e.g., irritation, conjunctival injection, epiphora, subconjunctival hemorrhage, canaliculitis, punctal stenosis, eyelid telangiectasia, eyelid edema, eyelid induration, eyelid erythema).

- **Additional safety assessments**

Corrected distance visual acuity, slit lamp biomicroscopy findings

Inclusion Criteria

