9.2.2. Corrected Distance Visual Acuity

Corrected distance visual acuity (CDVA) should be recorded with the participant's current spectacle correction or with the most current spectacle correction in a trial frame using the Early Treatment Diabetic Retinopathy Study (ETDRS) chart. The number of letters read correctly will be recorded. The CDVA should be collected at the screening examination and on the application day, both before and after the three randomized applications are administered, using the same spectacle correction used during the screening examination. If the CDVA is not believed to be maximal during the screening visit, pinhole visual

acuity should be recorded for this reading throughout the study or a manifest refraction should be performed.

Note: Repeated use of topical anesthetic and Schirmer testing may result in a transient decrease in CDVA.

Early Treatment Diabetic Retinopathy Study (ETDRS) Corrected Distance Visual Acuity

The equipment used will include a set of two Lighthouse Distance Visual Acuity Test charts (ETDRS Charts 1 and 2; Lighthouse Low Vision Products Precision Vision, Long Island, New York) and a retroilluminated box providing standardized chart illumination. Most of the room lights should be turned off during the visual acuity test as the box itself provides sufficient illumination for the examiner to record the test results. Additional light can have an adverse effect. With the box light off, not more than 15 foot-candles of light should fall on the center of the chart. A distance of exactly 4 meters is required between the participant's eyes and the visual acuity chart for the 4-meter test and a distance of exactly 1 meter is required for the 1-meter test.

The participant can be standing or sitting and will be asked to focus on an ETDRS visual acuity chart. Testing of all eyes should begin at the 4 meter test distance. The examiner should ensure that the head does not move forward or backward during testing. After careful instruction, testing should begin with the right eye using Chart 1.

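### Section 4.7 summarises CDVA only in three participant-level bands cut at 11 letters, so a device-eye loss of about one line is likely to be missed or not attributed to the device

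*Protocol*

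**What the plan says.** **What is collected.** Appendix B, Section 9.2.2 says "The number of letters read correctly will be recorded". The combined 4-metre and 1-metre totals, scored for each eye, "are entered on the worksheet as the final visual acuity letter score". Appendix A schedules CDVA at Baseline, Day 0, Day 3, Day 14 and Day 42.

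**What is analysed.** The first band in Section 4.7 is "the proportion of participants with an improvement of more than two lines (11 or more letters"). On the other two bands the section says that "a worsening of more than two lines and a change of two lines or less will be summarized". Every proportion is to carry an exact 95% interval, visit by visit. The unit is the participant. No mean or median letter change is named, and no comparison of the two eyes.

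**Related text.** Section 6.4 lists a loss of more than 10 letters as an anticipated adverse event. The note in 9.2.2 makes a rise of at least 0.22 logMAR from Day 0 an adverse event. Section 4.6 compares the device eye with the sham eye, but only for the effectiveness endpoints.

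**Size and aim.** The synopsis gives "Up to 13 participants, with a goal of 10 participants finishing study". Section 4.1 says "No sample size calculation has been performed", and Section 4.2 says "As a pilot, feasibility study, there is no clinical hypothesis".

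**The concern.** Of the two additional safety assessments in the synopsis (CDVA and slit-lamp findings), CDVA is the one with a numeric scale. One eye of each participant receives the device and the other a saline sham, so every participant supplies a control for acuity. Section 4.7 uses neither feature. A 10-letter loss, no change and a 10-letter gain all fall in the same middle band. A count of participants does not say which eye changed. The adverse event route does not recover smaller losses, because it uses the same threshold.

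At stake is what the pilot can say about acuity. It could report nearly everyone as changed by two lines or less while the device eye had lost about a line relative to the sham eye. Section 9.2.2 itself warns that repeated anaesthetic and Schirmer testing may lower CDVA transiently. A within-participant difference would remove whatever affects both eyes alike; a participant-level band does not.

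**Working it through.** The protocol states no power, SD or expected effect for CDVA, so there is no figure of its own to reproduce.

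**1. Do the cuts agree?** More than two lines is 11 or more letters (4.7), so a line is 5 letters. This matches the 30 letters on six lines in the 1-metre test of 9.2.2. At 0.02 logMAR per letter, 11 × 0.02 = 0.22 logMAR. The cuts in 4.7, 6.4 and 9.2.2 therefore coincide. The protocol is consistent here, and for the same reason the adverse event count adds nothing below 11 letters.

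**2. Precision of the planned summary.** With no participant in the worsening band, the exact (Clopper-Pearson) 95% upper limit is 1 − 0.025^(1/n):
- n = 10: 1 − 0.025^(1/10) = 30.8%
- n = 13: 1 − 0.025^(1/13) = 24.7%

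One of 10 gives 0.3% to 44.5%, and two of 10 give 2.5% to 55.6%.

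**3. What a one-line loss looks like in the bands.** If every device eye lost exactly 5 letters, all participants would be in the middle band and the table would match one with no change. With scatter, P(loss ≥ 11) = 1 − Φ((10.5 − mean loss)/SD). The SD of letter change per eye is assumed to be 3, 5 or 7 letters. For a mean device-eye loss of 5 letters:

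| SD | P(loss ≥ 11) | Expected of 10 | P(nobody), n = 10 | P(at most one), n = 10 | P(nobody), n = 13 |
|---|---|---|---|---|---|
| 3 | 3.3% | 0.3 | 71% | 96% | 64% |
| 5 | 13.6% | 1.4 | 23% | 60% | 15% |
| 7 | 21.6% | 2.2 | 9% | 33% | 4% |

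With small scatter the usual result is nobody over the cut. With larger scatter one or two participants cross, but then the sham eye can cross as well. With no mean change, 1 − Φ(10.5/5) = 1.8% and 1 − Φ(10.5/7) = 6.7%, which is 0.2 and 0.7 of 10. A count that is not split by eye cannot tell these apart.

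**4. Larger losses.** Over the same SDs, a mean loss of 8 letters puts 20% to 36% over the cut (2.0 to 3.6 of 10). A mean loss of 10 letters puts 43% to 47% over (4.3 to 4.7 of 10; 5.6 to 6.1 of 13), and the chance that nobody crosses is 0.3% or less.

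**5. Precision of the letter-scale summary.** The half-width of the 95% interval for the mean device-minus-sham change is t(0.975, n − 1) × SD_diff/√n, with SD_diff = SD × √(2(1 − r)). The assumed range is a per-eye SD of 4 with r = 0.5, giving SD_diff = 4, to a per-eye SD of 6 with r = 0, giving SD_diff = 8.5.
- n = 10: 2.262 × 4/√10 = 2.9 letters, to 2.262 × 8.5/√10 = 6.1 letters
- n = 13: 2.179 × 4/√13 = 2.4 letters, to 2.179 × 8.5/√13 = 5.1 letters

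Steps 2 and 5 describe different quantities, so the two widths should not be compared as numbers. Only step 5 addresses a systematic shift in the device eye.

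**The case against.** The strongest reply is that the bands are a coherent safety summary. They count individuals whose change reaches the level the protocol itself calls clinically significant, the cut is consistent throughout, and nothing in 4.7 forbids a mean change. A statistical analysis plan may add one. Part of this stands: the band table should stay, and it would be wrong to say the protocol rules out a letter-scale analysis. But 4.7 is not silent. It fixes the statistic, the cuts, the interval method and the timing, so that choice is open to review.

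The bands also do more than repeat the adverse event count, since they report gains and give intervals at each visit. The OSDI, completed for each eye and compared between eyes under 4.6, has items on blurred and poor vision. That is a coarser, symptom-based check and does not replace measured acuity.

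Two stronger readings are tempting, and the documents support neither.
- A reader might infer that the plan cannot show any loss up to two lines. That is true only of a uniform loss without scatter. Step 4 shows that mean losses of 8 to 10 letters would probably put about 2 to 6 participants over the cut.
- A reader might set the power of a paired t-test on letters against that of an exact paired test on the worsening band. The protocol plans neither test and has no hypothesis, so such power figures describe no planned analysis.

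The remedy also has limits. At the wide end of the assumed range the half-width at n = 10 is 6.1 letters, more than the one-line loss in question. It falls to about 5 letters when the SD of the difference is 7.

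**Conclusion.** The point holds in a limited form. Section 4.7 reduces a per-eye letter score to three participant-level bands, which loses the size and direction of changes within 10 letters and the device-versus-sham contrast. At 10 to 13 participants, a device-eye loss of about one line would probably go unseen, or appear as one or two participants over the cut without being tied to the treated eye. Losses nearer two lines would probably leave some trace, though inefficiently.

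The exact limits for 0/10 and 0/13 depend only on the sample size. The crossing probabilities and letter-scale half-widths rest on assumed SDs and correlations and on roughly normal changes, because the protocol gives no values. The consequence is modest, since this is a pilot without hypothesis tests, but the correction is cheap and worth making.

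**What to change.** Keep the three-band table in 4.7, report it separately for the device eye and the sham eye, and add:

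> At each follow-up visit, the change in ETDRS letter score from baseline will be summarised by eye (mean, SD, median, range), and the within-participant difference in change (device eye minus sham eye) will be presented with a 95% confidence interval.

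State which measurement is the baseline. CDVA is taken at screening and on Day 0, the adverse event note in 9.2.2 refers to Day 0, and 4.7 names no reference for the CDVA bands.

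The cost is one sentence and one more table from scores already recorded, with no new visits, procedures or participants. The downside is one more descriptive safety result, to be read without a multiplicity claim.
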